Title: High Dose Omega-3 Fatty Acids in the Treatment of Sport Related Concussions

NCT: 01814527

Completion Date: 4/25/2018

Methods

This study obtained IRB approval prior to enrollment of participants through East Carolina University and Medical Institutional Review Board. The study design was a randomized double-blind placebo-controlled trial using student's T test for analysis of continuous outcome variables. This study was conducted at East Carolina University over a 4 year period. The inclusion criteria for each subject were: must be a NCAA Division I student athlete at East Carolina University, must be 18 years old, have sustained a sport related concussion within the past 24 hours, and have a neurological exam not consistent with concern for an intracranial hemorrhage or other significant pathology. The exclusion criteria for each participant was: a recent prior concussion within the past 30 days, a history of moderate to severe TBI that has required hospitalization or resulted in prolonged signs and/or symptoms (>3 weeks), a known neurological diagnosis associated with impaired cognitive function other than attention deficit hyperactivity disorder or attention deficit disorder, a known allergy to algae, omega-3 fatty acid, or any component of the formulation, a known liver pathology or significantly elevated LFTs (greater than 3 x normal), a current lower extremity injury that will affect postural stability testing, subjects already routinely using omega-3/DHA supplementation, and subjects currently requiring anticoagulants, anti-platelets or any NSAIDs.

Once a student-athlete was diagnosed with a sport related concussion, and met the inclusion and exclusion criteria, the athlete met with the primary investigator and an IRB approved informed consent was obtained. The athlete then was randomly assigned to either high dose omega-3 fatty acid/DHA supplementation or placebo. Demographics of the athlete were obtained and include age, gender, sport, academic year, height, weight, BMI, history of prior concussion, migraines, learning disability, or psychiatric diagnosis. The experimental group was given a standardized dose of 2 grams (4 capsules) of omega-3 fatty acid/DHA for 30 days after onset of concussion. The placebo group was given an equal number of capsules. Both the omega-3 fatty acid/DHA capsules and placebo capsules were donated to East Carolina University for the purpose of this study by DSM Nutritional Products. The omega-3 fatty acid/DHA used in this study was derived from algae and therefore had no fish odor or after taste. The physician and the athletic training staff evaluating and clearing the athlete to return to activity were blinded. Each athlete underwent daily directly observed therapy by certified athletic trainers and daily symptom monitoring using the Symptom Evaluation scale found on the Sport Concussion Assessment Tool 2 (SCAT2). Symptoms were grouped into physical, cognitive, emotional and sleep categories with the total number of symptoms and symptoms severity score calculated for each category and overall.

Both groups underwent standard and usual care for concussed athletes at East Carolina University. East Carolina University employs a regimented return-to-play protocol for every student-athlete that has sustained a concussion (Figure 1). As part of their pre-participation physical, all student-athletes have a baseline computerized neuro-physical postural stability test using Bidex SD/BioSway and a computerized neurocognitive test using ImPact. At the time of

injury, a SCAT2 is administered by a certified athletic trainer, and the student-athlete is withdrawn from participation if they are symptomatic and/or have deficits noted. The same day a concussion is suspected a repeat Bidex postural stability test is administered and the student-athlete is given a detailed information sheet on instructions for monitoring and follow-up. A repeat Impact neurocognitive test is administered within 24 hours after the injury. The student-athlete is then seen and examined by a sports medicine physician to review the results, perform a clinical examination, and confirm the diagnosis. The student-athlete is then evaluated daily with a modified Symptom Evaluation Questionnaire found on the SCAT2 by an athletic trainer. When the student-athlete is asymptomatic with activities of daily living (ADLs) for 24 hours, he/she then begins a non-contact return to play protocol beginning with a supervised cardiovascular challenge. This includes 30 minutes of supervised light aerobic activity on a treadmill or stationary bike. If the athlete is asymptomatic with the cardiovascular challenge, then he/she can progress to noncontact sport specific drills the subsequent day. If the athlete is still doing well, he/she can progress their non-contact training drills and start light resistance training the following day. If the student-athlete remains asymptomatic through the non-contact activity progression, he/she then re-takes the computerized neurocognitive test, postural stability assessment and is re-evaluated by the physician. If the postural stability assessment and neurocognitive test are back to baseline the athlete is then cleared at the discretion of the treating sports medicine physician to return to full unrestricted activity. However, if a student-athlete continues to be symptomatic on day 7 both Impact and Bidex SD/BioSway evaluation will be re-administered. This will be repeated at 14 days and 30 days post-injury if the student-athlete continues to be symptomatic (Figure 1). The primary outcome of the study is the total number of days from onset of concussion it takes for the athlete to return to unrestricted full participation in their respective sport.

Results

A total of 62 student-athletes were enrolled and completed the study. 7 student-athletes were excluded from the analysis secondary to return to play greater than 30 days. Of those 7 student-athletes 6 were in the DHA cohort and 1 was in the placebo cohort. 55 student-athletes (33 male and 22 female) were used in the analysis. The demographics of the DHA cohort were: 19.7 ± 1.4 years of old, 60.9% male, 39.1% female, and a BMI of 27.7 ± 6.1 . The demographics of the placebo cohort were: 19.9 ± 1.4 years of age, 59.4% male, 40.6% female, and a BMI of 28.3 ± 6.1 . There was no statistically significant difference in age, gender, BMI, and sports distribution in the DHA vs the placebo cohort. Direct observed therapy of the intervention lead to a compliance rate of 84.2% in the DHA cohort and 83.0% in the placebo cohort. A previous history of concussion prior to the study was recorded and there was no statistical difference between the cohorts with the DHA cohort at 47.8% and the placebo cohort at 50%. The initial SCAT2 symptom severity score, an indicator of concussion severity, was recorded. The DHA cohort's initial SCAT2 symptom severity score was 42.7 ± 27.9 compared to the placebo cohort's initial SCAT2 symptom severity score of 49.9 ± 26.6 . Despite the placebo cohort's higher symptom

severity score this was not statistically significant. The primary outcome of this study was the number of days that the athlete required to return to play. The DHA cohort's return to play was 11.0 ± 4.8 days [95% CI 9.1,13.0] and the placebo cohort's return to play was 11.9 ± 5.4 days [95% CI 10.0,13.8], with a P value of 0.558 (Figure 2). The effect size was calculated to be 0.16 and a post hoc power analysis was calculated to be 0.09.

Figure 1: East Carolina University Concussion Management Standardized Protocol

[figure not shown]

Figure 2: Results

	DHA (n= 23)	Placebo (n=32)
Age (years)	19.7 ± 1.4	19.9 ± 1.4
Gender (male: female)	60.9%: 39.1%	59.4%: 40.6%
BMI (kg/m ²)	27.7 ± 6.1	28.3 ± 6.1
Compliance	84.20%	83.02%
History of Concussion	47.8%	50%
SCAT2 Symptom Severity Score	42.7 ± 27.9	49.9 ± 26.6
Return to Play (days) (P=0.558)	11.0 ± 4.8 [95% CI 9.1,13.0]	11.9 ± 5.4 [95% CI 10.0,13.8]

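### Seven athletes (6 DHA, 1 placebo) were dropped because their primary outcome exceeded 30 days; this favours DHA, and restoring them at a day-30 cap moves the difference from -0.9 to +2.5 days

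*Combined protocol and SAP*

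**What the plan says.** The combined protocol and SAP defines the endpoint at the end of Methods: "The primary outcome of the study is the total number of days from onset of concussion it takes for the athlete to return" to full participation. No upper limit is attached. The analysis method, in the first paragraph of Methods, is Student's "T test for analysis of continuous outcome variables", with no rule for capping, censoring or leaving out long values.

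The Results state: "A total of 62 student-athletes were enrolled and completed the study". They then state that "7 student-athletes were excluded from the analysis secondary to return to play greater than 30 days", and "Of those 7 student-athletes 6 were in the DHA cohort and 1 was in the placebo cohort". The analysis uses the remaining 55 athletes. Figure 2 gives 23 on DHA and 32 on placebo, with return to play of 11.0 ± 4.8 and 11.9 ± 5.4 days, P=0.558. The stated effect size is 0.16 and the post hoc power 0.09. No result for all 62 is given, and the number randomised to each arm is not stated.

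Thirty days appears in three other places in Methods: the supplementation period, the eligibility criterion on a recent earlier concussion ("The exclusion criteria for each participant was: a recent prior concussion within the past 30 days"), and the repeat testing schedule ("This will be repeated at 14 days and 30 days post-injury if the student-athlete continues to be symptomatic"). None of these limits the outcome or the analysis population.

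**The concern.** The exclusion is made after randomisation and is decided by the value of the primary outcome. These athletes were not ineligible, and the document counts them among those who completed. The eligibility criterion that mentions more than three weeks of signs or symptoms concerns an earlier brain injury, not the study concussion.

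Every removed value is above 30 days and every retained value is at or below 30, so deletion lowers the mean of any arm that loses athletes. If the arms lost similar shares, the effect on the difference might be small. Here the DHA arm loses about a fifth of its athletes and the placebo arm loses one, so the DHA mean falls much further. The direction and size of the reported difference are at stake, as is the unequal number of prolonged recoveries, which is disclosed but never analysed. The effect size, the P value and the baseline and compliance rows of Figure 2 also describe only the selected 55.

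**Working it through.** **Inputs.** From Results and Figure 2: DHA n=23, mean 11.0, SD 4.8; placebo n=32, mean 11.9, SD 5.4; excluded 6 and 1, each above 30 days. Assumption: tests are two-sided at 0.05 (not stated).

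**Reported result.** The difference is 11.0 - 11.9 = -0.9 days. The pooled SD is √[(22×4.8² + 31×5.4²)/53] = 5.16, so d = 0.9/5.16 = 0.174 and Student's P = 0.526. Rounding of the printed means and SDs allows P from about 0.48 to 0.58 and d from about 0.154 to 0.196, so the stated 0.558 and 0.16 are consistent. Power at d = 0.16 is 0.089, which matches the stated 0.09.

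**Arm totals.** 23+6 = 29 and 32+1 = 33; 29+33 = 62, the number enrolled.

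**All 62, capped at day 30.** Each of the seven contributes exactly 30, so no guess about their values is needed.

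- DHA mean: (23×11.0 + 6×30)/29 = 433/29 = 14.93.
- Placebo mean: (32×11.9 + 30)/33 = 410.8/33 = 12.45.
- Difference: +2.48 days. Rounding of the means moves it only between +2.39 and +2.57.
- Sum of squares in each arm, (n-1)s² + n(m-M)² + k(30-M)², with m and s the reported mean and SD, M the new mean and k the number restored: DHA 2224.7 (SD 8.91), placebo 1221.6 (SD 6.18).
- Pooled SD: √[(2224.7+1221.6)/60] = 7.58. Standard error: 7.58×√(1/29+1/33) = 1.93.
- 95% CI: 2.48 ± 2.00×1.93 = -1.38 to 6.34; p = 0.203 (Welch 0.214).

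**Uncapped days.** The seven values are not given. The table assumes one common value for all seven, which ignores variation among them. It shows how the difference behaves and is not an estimate.

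| Assumed day | Difference (DHA - placebo) | Student p | Welch p |
|---|---|---|---|
| 31 | +2.7 | 0.19 | 0.20 |
| 45 | +5.1 | 0.085 | 0.10 |
| 60 | +7.8 | 0.059 | 0.07 |

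**Break-even.** The uncapped difference is zero when the placebo athlete's value equals 33×(DHA mean) - 32×11.9.

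- Six DHA athletes at the 30-day limit: 33×14.931 - 380.8 = 111.9 days.
- All six at day 31: 118.8 days.
- All six at day 45: 214.3 days.

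Rounding of the reported means widens the first two from 112–119 to about 109–122 days. The uncapped mean would therefore still favour DHA only in an extreme case.

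**Not returned by day 30.** 6/29 = 20.7% v 1/33 = 3.0%.

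- Risk difference: 17.7 points (Newcombe 95% CI 1.3 to 35.5).
- Risk ratio: 6.8 (log-method 95% CI 0.87 to 53).
- Fisher p = 0.044; continuity-corrected chi-square p = 0.073.
- One athlete changed: 5/29 v 1/33 gives Fisher p = 0.089; 6/29 v 2/33 gives p = 0.13.

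**The case against.** The strongest defence is that 30 days is the supplementation period, so the analysis could be read as confined to the treatment window. That could justify stopping the clock at day 30. It does not justify deletion, because failure to return by day 30 is itself observed within the window. Figure 1 is not visible in the text reviewed, so the absence of a supporting rule is established only for the readable text.

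Several narrower objections stand:

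- The capped mean is not the outcome as defined. The +2.5 is a restricted mean difference, and the difference in total days cannot be computed from the document.
- The day-30 retest belongs to the university's usual care. It shows that slow recovery was foreseen, but it is not a trial analysis rule.
- Completing the study may mean completing 30 days, so the later return dates may not be held.
- The p-values under a common later value depend on an artificial assumption and should not be read as near-significant harm.

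The trial reports a null result, claims no efficacy and discloses the exclusions by arm, and the capped reanalysis is also non-significant. The test conclusion therefore probably does not change. The estimate and its sign do, and disclosing the counts does not correct them.

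**Conclusion.** The concern holds, and the analysis must be corrected. Excluding athletes on the value of the primary outcome, 6 of 29 against 1 of 33, biases the reported comparison toward DHA. Over 30 days the difference moves from -0.9 to +2.5 days (95% CI -1.4 to 6.3), which points to slower return on DHA but is compatible with no difference. This rests on the printed means and SDs and the derived arm totals, and on no assumption about the seven values. For uncapped days the sign depends on those values, although it favours DHA only if the one placebo athlete took well over 100 days while all six DHA athletes returned just after day 30. The imbalance in non-return by day 30 rests on seven events, is post hoc, and loses nominal significance if one athlete changes category. It should be analysed and reported, without being presented as evidence of harm.

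**What to change.** 1. Make the primary analysis all 62 athletes by randomised arm, and state the number randomised to each arm.
2. Where actual days to return are held for the seven, use them. This matches the defined outcome and the planned t test. Add the 30-day restricted mean as a sensitivity analysis, because a few long values can dominate a t test.
3. Where actual days are not held, keep the athlete as not returned at day 30. Replace the t test with the difference in mean time restricted to 30 days and its 95% CI, and add a log-rank test. A rank test with the seven ranked longest is an acceptable alternative. Record which analysis decides before rerunning.
4. Report return by day 30 by arm with its confidence interval, labelled post hoc.
5. Redo the Figure 2 baseline and compliance rows, the effect size and the P value on 29 and 33.
6. Keep the 55-athlete comparison only as a labelled post hoc sensitivity analysis.

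The cost is a reanalysis. The route in step 3 needs only day-30 status for the seven, which the Results already give; step 2 needs their return dates, if recorded. The result will be less favourable to DHA and probably still non-significant on the primary outcome.

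### Return to play is compared only by an unadjusted t test, although initial SCAT2 severity was recorded and plausibly predicts it; a post hoc ANCOVA is worth considering

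*Combined protocol and SAP*

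**What the plan says.** The opening paragraph of the Methods gives the whole analysis plan for the outcome: "using student's T test for analysis of continuous outcome variables". Neither the Methods nor the Results mentions a covariate, a regression model or stratified allocation.

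The Results state: "The initial SCAT2 symptom severity score, an indicator of concussion severity, was recorded". Figure 2 gives the score as 42.7 ± 27.9 on DHA (n=23) and 49.9 ± 26.6 on placebo (n=32). The only comment, after noting that placebo scored higher, is "severity score this was not statistically significant".

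The Methods describe two uses of the SCAT2 symptom scale. At injury, "a SCAT2 is administered by a certified athletic trainer"; afterwards there is "daily symptom monitoring using the Symptom Evaluation scale found on the Sport Concussion Assessment Tool 2 (SCAT2"). The Results do not say which of these is the initial score.

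The same section describes the route to the outcome. The graded steps begin "When the student-athlete is asymptomatic with activities of daily living (ADLs) for 24 hours". Full return then needs the activity steps completed, neurocognitive and postural tests back to baseline, and the athlete is "cleared at the discretion of the treating sports medicine physician".

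**The concern.** A baseline measure that predicts the outcome can sharpen a randomised comparison when it enters the model. The reason to expect prediction here lies in the design and not in the observed means: the return steps cannot start until symptoms have cleared for a day, so an athlete with a heavier initial symptom load plausibly starts them later. The trial already had the score, and it is the only injury-severity measure reported by arm.

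The significance remark does not help the reader. With 23 and 32 athletes a baseline test misses most moderate imbalances, and it is not a sound criterion for whether a prognostic variable belongs in the model.

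At stake are the precision of the estimate and how it is read given the severity mix of the athletes compared. The null conclusion is not at stake.

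**Working it through.** **Inputs.** All from the Results and Figure 2: n = 23 (DHA) and 32 (placebo); return to play 11.0 ± 4.8 and 11.9 ± 5.4 days; SCAT2 42.7 ± 27.9 and 49.9 ± 26.6; seven athletes excluded for return beyond 30 days, 6 DHA and 1 placebo. Assumed: a two-sided 5% level, and the within-arm correlation r between SCAT2 and days. The documents give neither.

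**1. The reported comparison fits an unadjusted t test.**
- Pooled SD of days = sqrt[(22×4.8² + 31×5.4²)/53] = 5.16. SE = 5.16 × sqrt(1/23 + 1/32) = 1.41 days.
- The printed means give 0.9/1.41 = 0.64, p = 0.53. The reported p is 0.558, which lies within the range that rounding of the means and SDs allows (0.48 to 0.58).
- "The effect size was calculated to be 0.16 and a post hoc power analysis was calculated to be 0.09". An effect size of 0.16 implies 0.16 × 5.16 = 0.83 days, and p = 0.558 also implies 0.83 days. Power at 0.16 is 0.089. All agree with an unadjusted analysis.

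**2. What the baseline test can show.**
- Pooled SD of SCAT2 = sqrt[(22×27.9² + 31×26.6²)/53] = 27.15. Gap = 49.9 - 42.7 = 7.2 points = 0.27 SD.
- SE = 27.15 × sqrt(1/23 + 1/32) = 7.42; p = 0.34; 95% CI -7.7 to 22.1. The statement of non-significance is correct.
- A gap would need to exceed 2.006 × 7.42 = 14.9 points (0.55 SD) to reach p < 0.05. Power to flag a true 7.2-point gap is 16%. The test says little about balance.

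**3. ANCOVA on the 55, by assumed r.**
- Shift = r × (5.16/27.15) × 7.2.
- SE = sqrt{[53 × 5.16² × (1 - r²)/52] × [1/23 + 1/32 + 7.2²/(53 × 27.15²)]}.

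| r | Shift (days) | Adjusted difference from 0.9 (from 0.83) | SE | Change in SE | p from 0.9 (from 0.83) |
|---|---|---|---|---|---|
| 0 | 0 | 0.90 (0.83) | 1.436 | +1.8% | 0.53 (0.57) |
| 0.2 | 0.27 | 0.63 (0.56) | 1.407 | -0.2% | 0.66 (0.69) |
| 0.3 | 0.41 | 0.49 (0.42) | 1.370 | -2.8% | 0.72 (0.76) |
| 0.5 | 0.68 | 0.22 (0.15) | 1.244 | -11.8% | 0.86 (0.91) |

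Differences are placebo minus DHA. Adjustment breaks even on precision at r = 0.19. For r from 0 to 0.7, p is never below 0.53 on either base.

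**4. Whether these figures carry over to all 62.** They do not. As an illustration, set each of the seven excluded athletes at 31 days, the minimum in whole days, and assume linearity with the pooled SDs above. An excluded athlete's expected SCAT2 is then the arm mean plus r × (27.15/5.16) × (31 - arm mean days).
- At r = 0.3 the slope is 1.58 points per day. DHA: 42.7 + 6 × 1.58 × 20.0/29 = 49.2. Placebo: 49.9 + 1.58 × 19.1/33 = 50.8. Gap = 1.6 points.
- The same steps give a gap of 7.2 at r = 0, 3.5 at r = 0.2, -0.3 at r = 0.4 and -2.2 at r = 0.5.
- Mean days become (23×11.0 + 6×31)/29 = 15.1 on DHA and (32×11.9 + 31)/33 = 12.5 on placebo, which reverses the direction.

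So the correlations at which adjustment would matter are also those at which the gap in all 62 shrinks or changes sign.

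**5. Cost if SCAT2 predicts nothing.** On 29 and 33 athletes the SE ratio is sqrt{(60/59) × [1 + g²/(60 × (1/29 + 1/33))]}, with g the gap in SD units. This is 1.008 at g = 0 and 1.018 at g = 0.265.

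**The case against.** The strongest reply is that this is a preference. The t test is valid, the result is null either way, and below r of about 0.19 adjustment costs a little precision. The benefit rests on a correlation nobody has reported, and the activity steps, the tests and physician discretion may all weaken it. This stands as a limit on weight. It does not remove the point, because adjusting for a recorded prognostic baseline is a recognised improvement whose possible loss is small.

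Two further objections stand in full. First, a reader might infer that SCAT2 was left out of the model because its gap was not significant. The Results never say so: they print both means and SDs, acknowledge that placebo was higher, and report the test without linking it to the choice of model. Second, the 7.2-point gap belongs to a sample selected on the outcome. If severity predicts slow return, the excluded athletes, mostly on DHA, would tend to have high scores, so the exclusion itself may have produced part of the gap.

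The doubt about timing is modest. The Methods place a SCAT2 at injury, and consent and allocation after diagnosis, so the natural reading is that the initial score precedes randomisation. It needs only confirmation.

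**Conclusion.** The point holds as a low-priority improvement, one to consider. The case for adjustment rests on the expected prognostic value of initial SCAT2 and not on the observed gap. On the 55, the SE would change by between about +2% and -12% for r from 0 to 0.5, and the estimate would move by at most half of its unadjusted SE (0.68/1.41 = 0.49 at r = 0.5). The conclusion would stay null. These figures assume the stated r, a linear relation and summary data rounded to one decimal. The adjusted differences are illustrations for the 55 only.

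Two stronger readings are tempting. One is that the unadjusted test is biased: randomisation makes it valid, and adjustment removes no average bias. The other is that milder injuries explain the apparent DHA advantage. The documents give no correlation to support this, and both the gap and the direction of the day difference may depend on the exclusion of 6 DHA and 1 placebo athletes. That exclusion is a separate and larger problem, which adjustment does not repair.

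**What to change.** Confirm that the initial score is the time-of-injury SCAT2 and precedes randomisation. Then:

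- Report the mean difference in return-to-play days from an ANCOVA with initial SCAT2 severity as a continuous covariate, labelled post hoc, beside the unadjusted result on the same athletes.
- Do this for the 55 and for all 62 where the days of the seven excluded athletes are available.
- Tabulate SCAT2 by arm for all 62.
- Delete the baseline significance statement and let the means and SDs stand.

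If a Cox model is used instead, the precision figures above do not apply, and its adjusted and unadjusted hazard ratios are not directly comparable.

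The work is to retrieve scores and days for seven athletes and fit one model. The statistical cost is one degree of freedom and, if SCAT2 does not predict return, an SE 1.8% larger on the 55 or about 0.8% to 1.8% larger on the 62.

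### The 95% interval printed for DHA return to play (9.1 to 13.0 days) is too narrow to be a t interval on 23 athletes; it matches a 1.96 interval

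*Combined protocol and SAP*

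**What the plan says.** The Methods section describes a randomised double-blind comparison "using student's T test for analysis of continuous outcome variables". Days from concussion to full return to sport is the primary outcome. No section says how confidence intervals for the arm means were to be computed.

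The Results section gives, for the active arm, "The DHA cohort's return to play was 11.0 ± 4.8 days [95% CI 9.1,13.0" and, for the control arm, "the placebo cohort's return to play was 11.9 ± 5.4 days [95% CI 10.0,13.8". The comparison is reported "with a P value of 0.558 (Figure 2"). Figure 2 repeats the same means, SDs and intervals and gives the arm sizes as 23 (DHA) and 32 (placebo). These agree with the total in the text: "55 student-athletes (33 male and 22 female) were used in the analysis".

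**The concern.** When the SD is estimated from only 23 athletes, the usual 95% interval for a mean multiplies the standard error by the t quantile on 22 degrees of freedom, 2.074, not by 1.96. The DHA interval looks too tight for that multiplier. If so, the active arm's primary-outcome row carries an interval that does not reach its labelled 95% level. It also sits beside a P value from a t test, so one row would mix two reference distributions without saying so. A reader who rebuilds the interval from the printed mean, SD and n will not recover it.

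**Working it through.** **Inputs** (Results section and Figure 2)

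- DHA: n = 23, mean 11.0, SD 4.8, printed limits 9.1 and 13.0. The n is supported by 60.9% male = 14/23, 47.8% with prior concussion = 11/23, and 23 + 32 = 55.
- Placebo: n = 32, mean 11.9, SD 5.4, printed limits 10.0 and 13.8.
- Formula: mean ± q × SD/√n, with q = 1.960 (normal) or the t quantile on n − 1 degrees of freedom.

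**1. DHA interval from the printed values.** SE = 4.8/√23 = 1.0009.

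| Multiplier | Half-width | Limits | Printed to one decimal |
|---|---|---|---|
| t(22), 2.0739 | 2.076 | 8.92 to 13.08 | 8.9 to 13.1 |
| Normal, 1.960 | 1.962 | 9.04 to 12.96 | 9.0 to 13.0 |

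Neither gives 9.1 to 13.0 exactly, so rounding of the mean and SD has to be allowed for.

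**2. Can rounding rescue the t interval?** The true mean lies between 10.95 and 11.05, and the true SD between 4.75 and 4.85.

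- Limits that print as 9.1 and 13.0 lie within 9.05 to 9.15 and 12.95 to 13.05. The half-width is therefore at most (13.05 − 9.05)/2 = 2.00.
- The smallest possible t half-width is 2.0739 × 4.75/√23 = 2.054, which exceeds 2.00.
- The highest possible t lower limit is 11.05 − 2.054 = 8.996, which prints as 9.0.
- To bring the half-width down to 2.00 the SD would have to be at most 2.00 × √23/2.0739 = 4.625, which does not round to 4.8.

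No admissible mean and SD give the printed limits with t(22).

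**3. Does the normal interval fit?** Its half-width runs from 1.96 × 4.75/√23 = 1.941 to 1.96 × 4.85/√23 = 1.982, inside the permitted 1.90 to 2.00. It prints as 9.1 to 13.0 for unrounded means from about 11.00 to 11.05. Example: mean 11.04 and SD 4.8 give 9.08 to 13.00.

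A mean slightly above 11.0 is plausible on other grounds:

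- The midpoint of the printed limits is (9.1 + 13.0)/2 = 11.05.
- The printed means give P = 0.526 and a standardised difference of 0.17, whereas the document reports 0.558 and states that "The effect size was calculated to be 0.16 and a post hoc power analysis was calculated to be 0.09".
- Assume that return to play was counted in whole days for every athlete. Means that print as 11.0 and 11.9 are then 252, 253 or 254 over 23 and 380, 381 or 382 over 32. Of the nine pairs, only 254/23 = 11.043 with 380/32 = 11.875 gives P = 0.558 in the equal-variance t test; the standardised difference is then (11.875 − 11.043)/5.159 = 0.16. With mean 11.043 and SD 4.8, the 1.96 interval is 9.08 to 13.01, printing as 9.1 to 13.0.

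**4. Placebo interval.** SE = 5.4/√32 = 0.9546. The normal interval is 10.03 to 13.77 and the t(31) interval (2.0395) is 9.95 to 13.85. Both print as 10.0 to 13.8, so the printed figures for this arm do not separate the methods. Under the whole-day assumption with mean 11.875, the t(31) lower limit would be at most 11.875 − 2.0395 × 5.35/√32 = 9.946, printing as 9.9. The placebo interval should therefore be checked too.

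**5. Size.** The printed half-width is (13.0 − 9.1)/2 = 1.95, and 1.95/2.076 = 0.94, so it is about 6% too narrow (full width 3.90 against 4.15 days). Under normality, the coverage of a 1.96 interval with 22 degrees of freedom is P(|t22| < 1.96) = 0.937.

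**The case against.** The strongest reply is that the Methods section prescribes Student's t for the analysis of outcomes, most naturally the between-arm comparison, and gives no rule for intervals around each arm mean. A large-sample interval then breaks no written rule. This is correct as far as it goes: the document omits the method rather than contradicting it. But the label of 95% still has to be met, and with an estimated SD and 23 observations a 1.96 multiplier does not meet it under the normal theory on which the t test rests.

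Second, 1.96 is not the only possible source. The t quantile on the pooled 53 degrees of freedom (2.006) with the arm's own SD, or a multiplier of 2, also prints as 9.1 to 13.0, but only in a corner of the rounding range. On a grid of about 10,000 mean and SD combinations, the normal interval fits 3,706, the multiplier of 2 fits 472 and the 53-df version fits 239. A percentile bootstrap is possible as well: in simulated right-skewed whole-day samples with the same n, mean and SD (an assumed shape), 62 of 300 gave exactly these limits. So the normal interval is the best simple explanation but is not proven. That the interval is not t(22) is certain on the printed figures.

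Third, the 93.7% is a normal-theory figure, and return times are skewed counts cut off at 30 days. Under an illustrative gamma distribution with the same mean and SD, coverage is about 93.3% for 1.96 and 94.5% for t. The gap of about one percentage point remains.

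Finally, the interval has little consequence, since separate arm intervals do not estimate the treatment effect. That stands, and it sets the priority of the point rather than its correctness.

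**Conclusion.** The point holds. With 23 athletes and an SD that rounds to 4.8, the printed DHA interval cannot be a t interval on 22 degrees of freedom. It is consistent with a 1.96 interval at an unrounded mean of about 11.00 to 11.05. The first statement needs only the printed n, mean, SD and limits with ordinary rounding. The attribution to 1.96 is an inference, and the coverage figure assumes normality.

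This is a minor error in the active arm's row for the primary outcome. It changes neither the reported P value nor the effect size, and the trial's null finding stands as far as this point goes.

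**What to change.** State in the Methods section how intervals for arm means are computed, and use the t quantile on n − 1 degrees of freedom. Recompute both arms from the raw data and correct the Results text and Figure 2 together. From the printed mean and SD the DHA interval becomes 8.9 to 13.1; if the unrounded mean is 11.04 it becomes 9.0 to 13.1 (8.96 to 13.12). For placebo, confirm that the same method was used even if the printed limits do not change.

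If the seven athletes excluded for return beyond 30 days are restored (23 + 6 = 29 DHA and 32 + 1 = 33 placebo), both intervals must be recomputed on those numbers by the same method. That is a separate question, and this correction need not wait for it.

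The cost is one recalculation entered in two places, and a slightly wider interval.
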